8.1. Informed consent

Each potential participant will be provided with a comprehensive explanation of the study procedures, and they will have the opportunity to ask questions and receive answers to any doubts they may have. The informed consent form must be signed by the participant or by a legally authorized representative before their participation in any of the study procedures. The documentation pertaining to the patient must demonstrate that consent was obtained before participation in the study. A copy of the signed informed consent form must be provided to the patient, and the original signed form must be retained at the study site.

8.2. Approval of ethical committee

The study will be conducted in accordance with international standards ISO 14:155, adhering to Good Clinical Practice and in compliance with the ethical principles outlined in the Declaration of Helsinki (64th WMA General Assembly, Fortaleza, Brazil, 2013). This protocol, the informed consent form, and all relevant information related to the study will be submitted to the appropriate Ethics Committee for evaluation and approval before the study commences. The current protocol poses no health risks to the participants. Any modifications to the protocol will be proposed to the Local Ethics Committee as an amendment request.

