3.3.1. Experimental group (virtual reality)

The rehabilitation team (comprising a physician, speech therapist, physiotherapist, and psychologist) will establish an individualized rehabilitation protocol for the recovery of sensorimotor and proprioceptive function in the upper limb. This protocol will involve exergaming exercises with virtual reality, totaling 50 minutes, conducted three days a week for four consecutive weeks. The rehabilitation protocol utilizing virtual reality will be carried out using the VRRS Khymeia system. This system will include exercises in semi-immersive virtual reality (utilizing the VRRS HandBox,

an advanced upper limb skeleton tracking device) and immersive virtual reality exercises (created with a Head Mounted Display device).

Rehabilitation sessions will take place at the Department of Rehabilitation Medicine and Neurorehabilitation at the IRCCS Institute of Neurological Sciences in Bologna.

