3.3.4. Post-Treatment Assessment

- a) Motricity Index Test (Bohannon, 1999)
- b) Fugl-Meyer Test (Fugl-Meyer et al., 1975)
- c) Box and Block Test (Mathiowetz et al., 1985)
- d) Functional Indipendence Measure (FIM) (Beninato et al., 2006)
- e) Multidimensional Assessment of Interoceptive Awareness (MAIA) (Machorrinho et al., 2019)

- f) Thumb Location Test (Rand, 2018) NO
- g) Rubber Hand Illusion test (Romano et al., 2021)
- h) STIMA test (Tessari et al., 2015) NO
- i) Attention: trial making test, matrici attentive, fluenza alternata.
- j) Client Satisfaction Questionnaire-8

4. Outcome

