4.1. Primary endpoint

In order to assess the effect that the proposed treatment has on the sensorimotor and proprioceptive impairment of the upper limb, a comparison is conducted between the baseline assessments (T0) and those performed at the end of the 4-week rehabilitation treatment (T1).

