4.2. Secondary endpoint

- To compare the effect of virtual reality rehabilitation for sensorimotor and proprioceptive deficits in the upper limb to conventional rehabilitation, a comparison is conducted between the assessments at T0 and T1 within the virtual reality treatment group (VR) and the group undergoing rehabilitation as per standard clinical practice (C).
- To assess patient satisfaction with the proposed experimental treatment, a validated questionnaire
 is administered to investigate patient satisfaction. The data are processed by calculating the mean,
 median, mode, and standard deviation for all 8 items. This approach allows for identifying the
 patient's overall considerations regarding the proposed treatment through a statistical summary
 that includes measures of central tendency (mean, median, mode) and data dispersion (standard
 deviation).

5. Data analysis

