5.2. Statistical analysis

The data analysis will be conducted using the Statistical Package for Social Science (SPSS version 26.0).

The preliminary data obtained from the pilot study will allow for estimating the variation in outcome measures between pre-test and post-test and between the treatment and control groups, providing insights for a potential subsequent trial with a larger sample.

The data will be analyzed based on the stated objectives, which include:

- Descriptive analysis of socio-demographic data for the experimental and control groups, including mean and standard deviation.
- The effect of the virtual reality rehabilitation protocol in the treated group will be assessed by comparing the scores of evaluation scales at pre-test and post-test. Data distribution will be tested using the Shapiro-Wilk test. The non-parametric Friedman test will be used in case of non-normal distribution, while ANOVA will be utilized in case of normal distribution. The significance level will be defined at $p \le 0.05$.
- The effect of the virtual reality rehabilitation protocol compared to the standard rehabilitation protocol will be assessed by comparing the scores of scales at T0 and T1 between the VR and C groups using the non-parametric Mann-Whitney test for independent samples.

6. Relevance

If the experimental hypotheses will be confirmed, the use of the virtual reality rehabilitation system could be implemented in routine clinical practice to rehabilitate sensorimotor integration in patients with stroke outcomes. An innovative approach employing virtual reality techniques aims not only to enhance patient treatment adherence but also to support proprioceptive and sensorimotor rehabilitation through the body illusion paradigm, which is not achievable in traditional rehabilitation. The enhancement of proprioceptive and sensorimotor aspects is considered crucial for the rehabilitation of neuromotor impairment. Therefore, by promptly implementing this type of intervention following a cerebrovascular event, one could hope for a faster and more effective functional recovery.

7. Feasibility

• The Rehabilitation Medicine and Neuro-rehabilitation Unit of the IRCCS Institute of Neurological Sciences in Bologna coordinates both the acute rehabilitation phase (with daily consultations at the Stroke Unit) and the sub-acute phase of the Stroke Clinical Pathway. Consequently, they daily admit patients with stroke outcomes at various stages of the

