8.3. Data policy

Adequate documentation will be maintained for all aspects related to the patient's clinical data, worksheets, nursing notes, adverse event notification forms, and study discontinuation forms. Personal data will be stored in compliance with GDPR guidelines. The results will be presented exclusively in aggregated and anonymized form.

9. Dissemination

The principal investigator commits to producing the final report, publishing all collected data as described in the protocol, and ensuring that the data are reported responsibly and consistently. In particular, the publication of data resulting from this study will occur irrespective of the obtained results. The transmission or dissemination of data through scientific publications and/or presentations at conferences, congresses, and seminars will only occur following the purely statistical analysis of the data or, in any case, in a completely anonymous form.

References

M. della salute. (2022.). No Title. ww.salute.gov.it

- Bohannon, R. W. (1999). Motricity index scores are valid indicators of paretic upper extremity strength following stroke. *Journal of Physical Therapy Science*, *11*(2), 59–61.
- Duncan, P. W., Goldstein, L. B., Horner, R. D., Landsman, P. B., Samsa, G. P., & Matchar, D. B. (1994). Similar motor recovery of upper and lower extremities after stroke. *Stroke*, 25(6), 1181–1188. https://doi.org/10.1161/01.STR.25.6.1181
- Explained, E. S. (2022). (n.d.). *No Title*. https://ec.europa.eu/eurostat/statistics-explained/index.php?title=Cardiovascular_diseases_statistics

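### Section 8.2 asserts no health risk, yet the protocol defines no way to elicit or report adverse events, incomplete sessions or withdrawals, and schedules the satisfaction measure only at T1

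*Protocol*

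**What the plan says.** Section 8.2, on the ethics committee submission, states: "The current protocol poses no health risks to the participants". No reason or figure is given. Section 8.3, on data policy, lists among the records to be kept "adverse event notification forms, and study discontinuation forms". Section 5.1 plans 20 patients, 10 per arm, and allows for 20% dropout.

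Under section 3.3.1 the VR arm receives exercises "totaling 50 minutes, conducted three days a week for four consecutive weeks", including "immersive virtual reality exercises (created with a Head Mounted Display device". Section 3.2 admits patients up to 85 years old and from 2 months after stroke.

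The primary endpoint (4.1) is defined thus: "a comparison is conducted between the baseline assessments (T0) and those performed at the end of the 4-week rehabilitation treatment (T1". The secondary endpoints (4.2) are the comparison between arms and satisfaction. The latter begins "To assess patient satisfaction with the proposed experimental treatment, a validated questionnaire", and the instrument, "Client Satisfaction Questionnaire-8", appears only in the post-treatment list in section 3.3.4.

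Section 6 says that the VR approach is meant to improve adherence to treatment. It adds that, if the hypotheses are confirmed, the system "could be implemented in routine clinical practice to rehabilitate sensorimotor integration in patients with stroke outcomes".

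**The concern.** A categorical statement of no risk does not fit with forms for adverse events and discontinuation, or with an allowance for one patient in five to drop out. At the least, the protocol should say why it expects no risk, or not say it.

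The practical consequence lies in measurement. A pilot of a device-based therapy is expected to tell the planners of the next trial whether patients get through the sessions and what happens to them there. Section 5.2 says that the data should inform a possible larger trial, and section 6 names adherence as an aim. Yet neither adherence nor tolerability is an assessment or an endpoint. Satisfaction is an endpoint, but it is scheduled at the end of treatment with no provision for patients who leave before then. The satisfaction summary may therefore describe completers only.

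**Working it through.** The protocol gives no power calculation and no risk figure to reproduce. The check is a comparison of sections, with some arithmetic for scale.

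**1. Where tolerability could have been placed**

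| Section | Content | Adverse events, session completion or withdrawals? |
|---|---|---|
| 3.3.3 (T0 list) | motor, proprioceptive, embodiment and cognitive tests | no |
| 3.3.4 (T1 list) | a subset of these, plus the CSQ-8 | no; satisfaction only |
| 4.1 | T0 to T1 change | no |
| 4.2 | comparison of arms; satisfaction | no; satisfaction only |
| 5.2 | descriptive demographics; within-group and between-group tests | no |
| 8.3 | list of records to be kept | forms named; no method of elicitation, timing or reporting |

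**2. Exposure** (sections 3.3.1, 3.3.2 and 5.1)

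- Sessions per patient: 3 per week × 4 weeks = 12, in each arm.
- Time per patient: 12 × 50 = 600 minutes.
- Scheduled VR sessions: 10 × 12 = 120. Both arms together: 20 × 12 = 240.

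Nothing in the protocol has anyone record how many of these sessions were completed.

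**3. Possible loss from the satisfaction endpoint**

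- Allowed dropout: 0.20 × 20 = 4 patients.
- The protocol does not divide these by arm. If equally divided (an assumption), 2 leave the VR arm and 10 − 2 = 8 answer the CSQ-8.
- Range: with 0 to 4 of the dropouts in the VR arm, 10 down to 6 patients answer.
- This assumes that a patient who stops early is not given the CSQ-8. The protocol does not say either way.

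**4. What a tolerability outcome could show with 10 VR patients**

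- With zero events, the one-sided 95% upper limit is 1 − 0.05^(1/10) = 0.259, about 26%. The two-sided Clopper-Pearson upper limit is 1 − 0.025^(1/10) = 0.308.
- The chance of seeing at least one affected patient is 1 − (1 − p)^10. The protocol gives no event rate, so the following values of p are assumptions: 5% gives 0.40, 10% gives 0.65 and 20% gives 0.89.

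The denominator is all treated VR patients. Restricting it to completers would be wrong, because a patient who stops through intolerance is an event.

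**The case against.** The case on the other side has force on several points.

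- **Events do have a record.** Section 8.3 keeps adverse event and discontinuation forms, nursing notes and worksheets. VR sessions take place in the department, and section 9 commits to publication whatever the results. A reader might infer that the pilot cannot show tolerability at all, or that events are recorded only when someone volunteers them. The protocol supports neither reading: it is silent on elicitation. What stands is that no method is defined, so completeness cannot be relied on.
- **Routine use is conditional.** Section 6 makes it depend on confirmed hypotheses, and section 5.2 looks to a larger trial. It would be wrong to say that the protocol proposes routine use outright.
- **The 26% limit does not measure the defect.** It follows from 10 patients, and the remedy leaves it unchanged. It shows only how little the pilot could exclude.
- **Dropouts need not be the patients who tolerated VR badly.** A reader might infer this, but section 5.1 gives a single overall allowance with neither cause nor arm.
- **Tolerability is not a stated objective, and an unseen statistical analysis plan may set the reporting.** This is true of tables and confidence limits. It does not answer the gap in collection: an analysis plan cannot summarise session completion or symptoms that nobody was asked to record. Satisfaction is a stated objective, so its timing is a matter for the protocol.
- **Risk information may stand in the consent pages,** which were removed before review. That would not remove the tension between sections 8.2 and 8.3.

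**Conclusion.** The point holds in a limited form. The unqualified sentence in section 8.2 sits badly with sections 8.3 and 5.1, and nothing in the protocol supports it. There is no defined way to elicit or report adverse events, incomplete sessions or withdrawals in either arm, although section 6 names adherence as an aim. The satisfaction endpoint may lose patients who stop early: between 0 and 4 of 10 in the VR arm under the stated dropout allowance, 2 if it is shared equally, and assuming that no CSQ-8 is given at discontinuation.

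The sample size, the type I error rate and the planned efficacy comparisons are unaffected. The documents do not show that VR causes harm in these patients, and this point does not claim that it does. The change should be made: it is cheap, and it protects a stated secondary endpoint as well as the record of safety.

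**What to change.** 1. Reconcile sections 8.2, 8.3 and 5.1. Remove the absolute statement or give its basis. Replacing it with a claim that risk is low would need support too, since the protocol contains no risk figure.
2. In sections 3.3.1 and 3.3.2, add one standard question on discomfort and adverse events after every session, in both arms, and a log of sessions completed, shortened or stopped with the reason.
3. In section 4.2, add these as a descriptive secondary outcome, reported by arm over all treated patients with exact confidence limits, together with withdrawals and their reasons.
4. In sections 3.3.4 and 4.2, give the CSQ-8 at discontinuation as well as at T1, and report how many patients answered at each.

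These changes concern measurement and reporting only. They leave the sessions, their schedule and the rules for stopping treatment as they are.

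Cost: text edits, and about one minute per session (an estimate), which is 240 × 1 = 240 minutes, or 4 hours, over the whole trial if all sessions take place. More minor symptoms will be recorded. The report should also say that zero events in 10 VR patients would leave rates up to about 26% compatible with the data.

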8.3. Data policy

Adequate documentation will be maintained for all aspects related to the patient's clinical data, worksheets, nursing notes, adverse event notification forms, and study discontinuation forms. Personal data will be stored in compliance with GDPR guidelines. The results will be presented exclusively in aggregated and anonymized form.

9. Dissemination

The principal investigator commits to producing the final report, publishing all collected data as described in the protocol, and ensuring that the data are reported responsibly and consistently. In particular, the publication of data resulting from this study will occur irrespective of the obtained results. The transmission or dissemination of data through scientific publications and/or presentations at conferences, congresses, and seminars will only occur following the purely statistical analysis of the data or, in any case, in a completely anonymous form.

References

M. della salute. (2022.). No Title. ww.salute.gov.it

- Bohannon, R. W. (1999). Motricity index scores are valid indicators of paretic upper extremity strength following stroke. *Journal of Physical Therapy Science*, *11*(2), 59–61.
- Duncan, P. W., Goldstein, L. B., Horner, R. D., Landsman, P. B., Samsa, G. P., & Matchar, D. B. (1994). Similar motor recovery of upper and lower extremities after stroke. *Stroke*, 25(6), 1181–1188. https://doi.org/10.1161/01.STR.25.6.1181
- Explained, E. S. (2022). (n.d.). *No Title*. https://ec.europa.eu/eurostat/statistics-explained/index.php?title=Cardiovascular_diseases_statistics
